## 9.2 Exclusion Criteria

An individual who meets any of the following criteria will be ineligible for participation in this study:

1. Any one of the following requiring medical attention within 14 days prior to signing the informed consent form (ICF):
  - Vaso-occlusive crisis (VOC)
  - Acute chest syndrome (ACS)
  - Splenic sequestration crisis
  - Dactylitis
2. Requires chronic transfusion therapy
3. RBC transfusion within 60 days of signing the ICF
4. Renal dysfunction requiring chronic dialysis or creatinine  $\geq 1.5$  mg/dL.
5. Hepatic dysfunction characterized by alanine aminotransferase (ALT)  $>4\times$  upper limit of normal (ULN) for age.
6. Clinically relevant cardiac abnormality, in the opinion of the Investigator, such as:
  - Hemodynamically significant heart disease, e.g., congenital heart defect, uncompensated heart failure, or any unstable cardiac condition
  - An arrhythmic heart condition requiring medical therapy
7. QTcF  $>450$  msec, congenital long QT syndrome, second- or third-degree heart block at rest (with the exception of asymptomatic Mobitz type I second degree heart block).
8. Received an investigational drug within 30 days or 5 half-lives, whichever is longer, of signing the ICF.
9. Heavy smoker (defined as smoking more than 10 cigarettes/day or its nicotine equivalent including e-cigarettes).
10. Unlikely to comply with the study procedures.
11. Other medical, psychological, or addictive condition that, in the opinion of the Investigator, would confound or interfere with evaluation of safety and/or PK of the investigational drug, prevent compliance with the study protocol, or preclude informed consent.
12. Any condition affecting drug absorption, such as major surgery involving the stomach or small intestine (prior cholecystectomy is acceptable).

13. History of malignancy within the past 2 years prior to treatment Day 1 requiring chemotherapy and/or radiation (with the exception of local therapy for non-melanoma skin malignancy).
14. Clinically significant bacterial, fungal, parasitic, or viral infection currently receiving or that will require therapy.
  - Participants with acute bacterial infection requiring antibiotic use should delay screening until the course of antibiotic therapy has been completed and the infection has resolved, in the opinion of the investigator.
  - Known active hepatitis A, B, or C infection or human immunodeficiency virus (HIV)-positive; known active
  - Known active malaria.
15. Pregnant patients
16. Evidence of abnormal high blood flow velocities on TCD of 200 cm/sec or more

### **9.3 Lifestyle Considerations**

During this study, participants are asked to:

- Refrain from using herbal medications (e.g., St. John's Wort), or medications that are sensitive cytochrome CYP3A4 substrates or CYP3A4 modulators, such as fluconazole.

### **10. Vulnerable Populations**

There are no restrictions in the inclusion or exclusion criteria in regard to race, ethnicity, or gender. However, SCD is more common in certain ethnic groups including individuals of African descent such as African Americans and Hispanic-Americans from Central and South America and individuals of Middle Eastern, Asian, Indian, and Mediterranean descent. Thus, we anticipate that our cohort will be reflective of this.

This research includes individuals who are not yet adults. Safeguards are in place to protect their rights and welfare. This study research is consistent with the Declaration of Helsinki in that the research is necessary to promote the health of children with sickle cell disease.

Children will not be enrolled without the informed consent of parents and the assent (or consent) of the child per IRB/REB/local ethics committee policies and guidelines.

Declining to participate in the research will not affect their care.

### **11. Local Number of Participants**

Approximately 50 subjects are expected to be accrued in this research. The anticipated accrual rate is 5-8 subjects per month.

### **12. Recruitment Methods**

#### **12.1 Subject Identification**

Potential participants will be recruited from outpatient sickle cell clinic at Children's Healthcare of Atlanta. Providers, including physicians, advanced practice providers (APPs-nurse practitioners

or physician assistants), or genetic counselors will identify potential participants based on their diagnoses at the time of their scheduled clinical visits.

Patients under the care of providers at Children's Healthcare of Atlanta (CHOA) sites who have sickle cell disease may be approached for enrollment at any time after being diagnosed.

We plan to enroll children with sickle cell disease with any mix of male or female gender, ranging in age from 4 to 30 years.

IRB approved study team members will identify potential candidates through medical record review. Patients and families of the Children's Healthcare of Atlanta inpatient and outpatient sickle cell disease clinics will be contacted by a study team member prior to their scheduled appointment. Patients and families may be approached in the clinic or via a phone call.

## **12.2 Screen Failures**

Individuals who do not meet the criteria for participation in this trial (screen failure) because recent vaso-occlusive crisis (VOC), acute chest syndrome (ACS), splenic sequestration crisis, or dactylitis may be rescreened. Rescreened participants should be assigned the same participant number as for the initial screening.

Individuals who do not meet the criteria for participation in this study (screen failure) because hydroxyurea dose or hemoglobin had not been stable for 3 months may be rescreened. Rescreened participants should be assigned the same participant number as for the initial screening.

Screen failures are defined as participants who consent to participate in the clinical trial but are not entered in the study. A minimal set of screen failure information is required to ensure transparent reporting of screen failure participants, to meet the Consolidated Standards of Reporting Trials (CONSORT) publishing requirements and to respond to queries from regulatory authorities. Minimal information includes demography, screen failure details, eligibility criteria, and any serious adverse event (SAE).

## **13. Withdrawal of Participants**

### **13.1 Discontinuation of Study Intervention**

At any point in the study, the child or parents can withdraw from the study. Discontinuation from voxelotor treatment will end participation in the study.

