## 5.2 Schedule of Assessments (SoA)

FDNIRS/DCS and TCD measurements will be made on D1, or within the screening period depending on researcher availability. For the 4w, 8w, and 12w and end of study visits, the time point given spans a window of +/- 7 days. For patients continuing commercial voxelotor after 12w, the end of treatment (12w) visit will also serve as the end of study visit. Patients who will not continue commercial voxelotor after 12w will complete an end of study visit up to 8 weeks after last study dose.

	Screening (up to 28 days)	Treatment				End of Study (up to 8 wks post-treatment)
		D1 (+/- 7d)	4w (+/- 7d)	8w (+/- 7d)	12w (+/- 7d)	
Consent/Accent	X					
Inclusion/Exclusion Criteria	X					
Medical History & PE	X	X			X	
Height, weight	X				X	X
Vital signs, pulse oximetry	X	X	X	X	X	X
CBC diff, retic	X	X	X	X	X	X
CMP & LDH	X				X	X
Hb Electrophoresis	X				X	
Hb morphology	X	X	X	X	X	X
RBC Health		X			X	
FDNIRS/DCS (performed by [name] Lab staff)		X	X		X	
Transcranial Doppler ultrasound (TCD)	(X)	X			X	
Pregnancy testing (for females of child bearing potential)	X					
Adverse event reporting	X	X	X	X	X	X
Drug dispensing		X	X	X	X	

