### **5.5 Time Period and Frequency for Event Assessment and Follow-up**

The occurrence of an adverse event (AE) or serious adverse event (SAE) may come to the attention of study personnel during study visits and interviews of a study participant presenting for medical care, or upon review by the study PI.

All AEs including local and systemic reactions not meeting the criteria for SAEs will be captured on the appropriate study database form. Information to be collected includes event description, time of onset, clinician's assessment of severity, relationship to study product (assessed only by those with the training and authority to make a diagnosis), and time of resolution/stabilization of the event. All AEs occurring while on study must be documented appropriately regardless of relationship. All AEs will be followed to adequate resolution.

Any medical condition that is present at the time that the participant is screened will be considered as baseline and not reported as an AE. However, if the study participant's condition deteriorates at any time during the study, it will be recorded as an AE.

Changes in the severity of an AE will be documented to allow an assessment of the duration of the event at each level of severity to be performed. AEs characterized as intermittent require documentation of onset and duration of each episode.

The PI or study coordinator will record all reportable events with start dates occurring any time after informed consent is obtained until 7 (for non-serious AEs) or 30 days (for SAEs) after the last day of study participation. At each study visit, the investigator will inquire about the occurrence of AE/SAEs since the last visit. Events will be followed for outcome information until resolution or stabilization.

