### **5.10 End of Study**

A participant is considered to have completed the study if he or she has completed all phases of the study including the last visit or the last scheduled procedure shown in the Schedule of Activities (SoA). For patients continuing commercial Voxelotor after 12w, the end of treatment (12w) visit will also serve as the end of study visit. Patients who will not continue commercial Voxelotor after 12w will complete an end of study visit up to 8 weeks after last study dose.

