### **13.2 Participant Discontinuation/Withdrawal from the Study**

Participants are free to withdraw from participation in the study at any time upon request. An investigator may discontinue or withdraw a participant from the study for the following reasons:

- Pregnancy
- Significant study intervention non-compliance
- If any clinical adverse event (AE), such as hypersensitivity to the study drug, laboratory abnormality, or other medical condition or situation occurs such that continued participation in the study would not be in the best interest of the participant
- If the participant meets an exclusion criterion (either newly developed or not previously recognized) that precludes further study participation
- Disease progression which requires discontinuation of the study intervention

The reason for participant discontinuation or withdrawal from the study will be recorded on the Case Report Form (CRF). Subjects who sign the informed consent form and subsequently withdraw, or are withdrawn or discontinued from the study, will not be replaced.

Once dosed, participants who discontinue/withdraw the study will not be replaced. We estimate 40 subjects will be sufficient to achieve the primary, secondary, and exploratory endpoints. Our target sample size of 50 allows for approximately 20% drop out rate. This dropout rate far exceeds the actual dropout rate in the large multicenter Phase 2a study of voxelotor use in pediatrics (GBT440-007).

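### Stopping voxelotor ends study participation, so a participant who stops before Week 12 has no scheduled safety visit or post-dose chemistry and a shorter window for new adverse events than a Week 12 completer who stops

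*Combined protocol and SAP*

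**What the plan says.** Five places in the combined protocol and SAP, and Attachment A, bear on what happens after the last dose.

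- **Section 13.1:** "Discontinuation from voxelotor treatment will end participation in the study".
- **Section 13.2** lists the grounds on which the investigator may withdraw a participant. One entry begins "If any clinical adverse event (AE), such as hypersensitivity to the study drug, laboratory abnormality, or other medical condition". Significant non-compliance and pregnancy are also listed. The reason for leaving is recorded on the case report form.
- **Section 5.2 (Schedule of Assessments):** "Patients who will not continue commercial voxelotor after 12w will complete an end of study visit up to 8 weeks after last study dose". For the other completers, "For patients continuing commercial voxelotor after 12w, the end of treatment (12w) visit will also serve as the end of study visit". The End of Study column holds height and weight, vital signs, blood count, CMP and LDH, Hb morphology and AE inquiry. CMP and LDH are marked at three points only: screening, Week 12 and End of Study.
- **Section 5.10** repeats the same rule: "Patients who will not continue commercial Voxelotor after 12w will complete an end of study visit up to 8 weeks after last study dose".
- **Section 5.5** sets recording of new events "until 7 (for non-serious AEs) or 30 days (for SAEs) after the last day of study participation", with inquiry about events at each study visit. It adds: "All AEs will be followed to adequate resolution".
- **Attachment A, item 7,** sets a 28-day SAE reporting period to the supplier, or longer if the protocol says so. SAEs with a suspected causal link stay reportable after that.

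The plan describes no early-termination visit.

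**The concern.** In most trials, stopping the drug and leaving the study are separate events, so that harms that appear or resolve after a toxicity-related stop are still collected. Section 13.1 merges the two. The off-drug visit is worded for people who have reached Week 12, and the AE windows run from the last day of participation. Taken together, the shorter follow-up and the lack of a scheduled laboratory check fall on the group that includes those who stopped because of a suspected harm.

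The stake is mainly safety data: new off-drug events and laboratory recovery may go unrecorded in that group. There is also a reporting consequence. Participants who stop early have no Week 12 optical measurement, so the Week 12 result describes those who stayed on drug.

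**Working it through.** **Inputs.** Last study dose taken as day 0. For an early stopper, the day drug is stopped is taken as the last day of participation (Section 13.1 read literally). End of Study visit: up to 8 weeks after the last study dose (Sections 5.2 and 5.10). Windows after participation ends: 7 days for non-serious AEs, 30 days for SAEs (Section 5.5). Sample size: 40 sufficient, 50 targeted, about 20% dropout (Section 13.2).

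**Step 1. The plan's own dropout figure.** 40 / (1 − 0.20) = 50, which matches the target. The allowance is therefore 50 × 0.20 = 10 participants.

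**Step 2. Time covered after the last study dose.**

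- Stops before Week 12: 7 days for new non-serious AEs and 30 days for new SAEs.
- Completes Week 12 and stops: visit at up to 8 × 7 = 56 days, then 56 + 7 = 63 days and 56 + 30 = 86 days at most. If the ±7-day visit window in Section 5.2 is added in full, these become 70 and 93 days.
- Completes Week 12 and continues commercial drug: participation ends at the Week 12 visit, then 7 and 30 days.

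**Step 3. Scheduled assessments, from the Section 5.2 table.**

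| Group | Scheduled CMP and LDH after first dose | Scheduled visit after last study dose | New non-serious AEs | New SAEs |
|---|---|---|---|---|
| Stops before Week 12 | 0 | none, read literally | 7 days | 30 days |
| Completes, then stops | 2 (Week 12, End of Study) | at up to 56 days | up to 63 days | up to 86 days |
| Completes, continues commercial drug | 1 (Week 12) | none; Week 12 serves as End of Study | 7 days after Week 12 visit | 30 days after Week 12 visit |

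The AE windows alone do not set early stoppers apart, because completers on commercial drug have the same 7 and 30 days. The chemistry column does: early stoppers are the only dosed group with no scheduled CMP and LDH after the first dose. They do have blood counts at any Day 1, Week 4 or Week 8 visit they attended before stopping.

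**Step 4. Duties that outlast participation.** Section 5.5 requires known events to be followed to resolution or stabilization, and Section 5.8 requires pregnancies to be followed to an outcome. Section 13.1 ends participation without naming a visit that supports either duty.

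**The case against.** The strongest reply is that the plan is less bare than it looks, and much of that reply stands.

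- A reader might infer that all AE collection stops after 7 days. It does not. That limit covers only new non-serious events; new SAEs have 30 days, the event that led to the stop is followed to resolution or stabilization, and causally suspected SAEs stay reportable to the supplier.
- A reader might infer that early stoppers are expressly denied the End of Study visit. The schedule's column header speaks only of up to 8 weeks post-treatment, and the visit is timed from the last study dose. Neither excludes them. The exclusion comes from the after-Week-12 wording combined with Section 13.1, so the text is ambiguous on this point.
- A reader might quote a ninefold gap, 63 / 7 = 9. That sets a maximum against a fixed value. A completer seen one week after the last dose would have 7 + 7 = 14 days, a ratio of 2.
- A reader might infer that no chemistry result would exist. The plan shows only that none is scheduled. Section 5.3 lets clinical samples serve the study, and a participant stopped for a laboratory abnormality has had a laboratory result.
- Section 4.1 allows the dose to be reduced or held for AEs, with resumption later. A hold need not trigger Section 13.1; the point concerns permanent discontinuation.
- A reader might conclude that the Week 12 optical result is invalid, or that off-drug scans are required. Section 17.2 calls the results descriptive, and the hypothesis concerns change as hemoglobin rises on voxelotor. An on-treatment measurement is a defensible target, and someone who stops after Week 4 may already have given the Week 4 primary measurement.

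The reply does not remove the core gap. No section states which visit applies after an early stop, and the literal reading provides none.

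**Conclusion.** The point holds as a gap in safety data collection, and it should be fixed. Read literally, a participant who stops before Week 12 has no further scheduled safety visit and no scheduled CMP and LDH after the first dose. New events are recorded for 7 days (non-serious) or 30 days (serious), against at most 63 and 86 days for a Week 12 completer who stops.

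At most about 10 of 50 participants would be affected. That ceiling assigns the whole 20% allowance to stopping drug, although the allowance covers every cause of dropout. Section 13.2 says 20% far exceeds the dropout seen in an earlier pediatric study of the drug, so the true number may be well below 10.

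The conclusion rests on two assumptions: that Section 13.1 is applied as written, and that the after-Week-12 wording in Sections 5.2 and 5.10 is meant. If the sponsor intended early stoppers to have the End of Study visit, the defect is one of wording, and the same clarification settles it.

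**What to change.** Reconcile Sections 5.2, 5.5, 5.10, 13.1, 13.2 and Attachment A (item 7) so that ending study drug is separated from ending safety data collection. In particular:

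- Apply the End of Study visit already defined in Section 5.2 to dosed participants who stop before Week 12, unless consent is withdrawn, and run the existing 7-day and 30-day windows from that visit.
- Report the Week 12 optical results as on-treatment results, with the number of early stoppers and their reasons. Section 13.2 already requires the reason to be recorded.

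The cost is protocol wording plus one existing visit for a few participants, at most about 10, some of whom may decline. No new procedure is needed, further optical sessions off drug are not asked for, and nothing here changes when or why drug is stopped.

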### **13.2 Participant Discontinuation/Withdrawal from the Study**

Participants are free to withdraw from participation in the study at any time upon request. An investigator may discontinue or withdraw a participant from the study for the following reasons:

- Pregnancy
- Significant study intervention non-compliance
- If any clinical adverse event (AE), such as hypersensitivity to the study drug, laboratory abnormality, or other medical condition or situation occurs such that continued participation in the study would not be in the best interest of the participant
- If the participant meets an exclusion criterion (either newly developed or not previously recognized) that precludes further study participation
- Disease progression which requires discontinuation of the study intervention

The reason for participant discontinuation or withdrawal from the study will be recorded on the Case Report Form (CRF). Subjects who sign the informed consent form and subsequently withdraw, or are withdrawn or discontinued from the study, will not be replaced.

Once dosed, participants who discontinue/withdraw the study will not be replaced. We estimate 40 subjects will be sufficient to achieve the primary, secondary, and exploratory endpoints. Our target sample size of 50 allows for approximately 20% drop out rate. This dropout rate far exceeds the actual dropout rate in the large multicenter Phase 2a study of voxelotor use in pediatrics (GBT440-007).

### **13.3 Lost to Follow-Up**

A participant will be considered lost to follow-up if he or she fails to return for scheduled visits and is unable to be contacted by the study site staff.

The following actions must be taken if a participant fails to return to the clinic for a required study visit:

- The site will attempt to contact the participant and reschedule the missed visit within 1-2 weeks and counsel the participant on the importance of maintaining the assigned visit schedule and ascertain if the participant wishes to and/or should continue in the study.
- Before a participant is deemed lost to follow-up, the investigator or designee will make every effort to regain contact with the participant (where possible, 3 telephone calls and, if necessary, a certified letter to the participant's last known mailing address or local equivalent methods). These contact attempts should be documented in the participant's medical record or study file.
- Should the participant continue to be unreachable, he or she will be considered to have withdrawn from the study with a primary reason of lost to follow-up.

## **14. Risks to Participants**

Treatment with this study drug may also involve risks that we currently don't know about.

As of November 2019, commercial Oxbryta (voxelotor) was approved for treatment of sickle cell disease in adults and pediatrics 12 years and older. In December 2021, the indication was modified to include pediatrics 4 years and older.

The most common adverse reactions (incidence >10%) are headache, diarrhea, abdominal pain, nausea, fatigue, rash, and pyrexia. Other reported side effects include symptoms like a common cold (upper respiratory tract infection), pain (including pain in joints, stomach, chest, and back) and vomiting.

All of these side effects were also reported by people who took placebo (a sugar pill, containing no voxelotor). Adults and children had sickle cell pain crises during previous and current studies with voxelotor, but they occurred as often as in people who received placebo (sugar pill, containing no voxelotor); most of these events were thought to be related to SCD. Acute chest syndrome and priapism also occurred on other studies with voxelotor – these events were less common and are known to be related to SCD. Overall, the side effects observed in adults and children were similar.

Uncommon side effects (occurring in 0.1 % to 1% of people; between 1 and 10 in a thousand people): Allergic reactions that the study doctors thought were caused by voxelotor were also reported in one person with SCD. Symptoms of this allergic reaction included face swelling and fever. Symptoms went away after the study drug was stopped.

Unknown risks: It is possible that your SCD symptoms will not improve during the study or may even worsen. Treatment with this study drug may also involve risks to your future health that we currently don't know about.

Interaction with other medications: The effects of the study drug may change when taken with other drugs. Among these are carbamazepine, phenytoin, rifampin and St. John's Wort

Blood draw: The risks of drawing blood from a vein include fainting and pain, bruising, swelling, or rarely infection at the needle site. These discomforts are brief and transient.

DCS/NIRS test: The light used in the DCS/NIRS sensor delivers less power than the energy your child would receive from the sun on an outdoor walk on a sunny day. This energy is also below the American National Standards Institute (ANSI) light levels and is in compliance with the United States Food and Drug Administration (FDA). See **Appendix** for more information. Children with sensitive skin might have minor temporary skin irritation from contact with the optical sensor on the forehead.

